3. INTRODUCTION

3.1. Rationale for the Study

Central melanocortin signaling is the central element of energy homeostasis [Holland 2019]. In patients with hypothalamic lesions, leptin signaling is often disturbed and as a result melanocortin signalling is reduced [Enriori 2016; Roth 2010; Roth 1998; Patel 2002; Shaikh 2008]. Imaging studies in humans and rodents models show that lesions of the ventromedial nucleus of the hypothalamus (VMN) and the region of the arcuate nucleus (ARC), are more often associated with hyperphagia and excessive weight gain [Ahmet 2006; DeVile 1996; Roth 2011; Daousi 2005; Holmer 2010; Elfers 2011].

Hypothalamic obesity (HO) is a severe obesity that arises from mechanical hypothalamic insults (eg, tumors, tumor resections, radiotherapy treatment). Lesions of hypothalamus can derive from various types of tumors (craniopharyngiomas, gliomas, pituitary adenomas, hamartomas) and surgeries and radiotherapies for the treatments of the tumor itself. Literature reports that patients with craniopharyngioma are less physically active than controls with comparable body mass indices (BMIs) [Harz 2003]. Moreover, they display higher degree of hyperleptinemia and hyperinsulinemia when compared to individuals with normal BMIs. Alpha-melanocortin-stimulating hormone (α -MSH) can be detectable in blood, and its levels can change depending on different energy states [Enriori 2016]; however, in patients with craniopharyngioma or post-surgical treatment for it, α -MSH levels are significantly reduced [Roth 2010; Roth 2011]. Reduced serum α -MSH levels suggest melanocortin pathway deficiency, which might explain lower energy expenditure in peripheral tissues due to reduced fat and muscle fatty acid oxidation [Roth 2010; Roth 2011; An 2007].

In a rat model of “combined medial hypothalamic lesion” or CMHL rat model for HO [Roth 2011], Roth et al found that the characteristic metabolic changes of human HO were recapitulated when the lesion included the rat ARC. In this rat model, α -MSH levels are reduced [Roth 2011], similar to patients with craniopharyngioma [Roth 2010].

Additionally, an MC3/4 receptor agonist, MTII 1mg/kg/d intraperitoneally over a period of 14 days, resulted in a robust reduction of weight gain in CMHL rats without rebound/tachyphylaxis (-17.2% vs. saline injected controls) [Roth 2012]. Taken together, these preclinical and clinical findings offer a rationale for a novel melanocortin treatment in patients with HO to compensate for potentiate the defective leptin signaling.

Setmelanotide, a potent agonist of the human melanocortin 4 receptor (MC4R) [Sharma 2019], has been studied in relevant genetic models of obesity, and in clinical studies. In mice, leptin-receptor deficient Zucker fa/fa rats (a rodent model of genetic obesity impacting the MC4R pathway) and Magel2-null mice (a mouse model for Prader-Willi syndrome), treatment with a melanocortin receptor agonist reduced both body weight and food intake [Bischof 2016; Hwa 2001]. These data demonstrate that setmelanotide is effective in these models of monogenic and syndromic obesity. In humans, homozygous mutations of the proopiomelanocortin (POMC) and leptin receptor (LEPR) obesity were successfully treated by setmelanotide [Kuhnen 2016; Clement 2018]. Overall, nonclinical and clinical data demonstrate that setmelanotide restores normal hunger, satiety, and energy expenditure regulation, leading to profound reduction of excess weight, in essence as a form of “replacement therapy”.

Putting together these results, MC4Rs expressed in the paraventricular nucleus (PVN) of the hypothalamus play a paramount role for body-weight regulation and for the leptin–melanocortin weight regulatory pathway of the hypothalamus [Kuhnen 2019]. Although setmelanotide has not been tested in a model of HO, given its role in restoring POMC pathway in POMC/LEPR deficient patients and the reported damage of the POMC pathway in the HO syndrome, this proposed study will investigate whether setmelanotide can be employed to recover melanocortin signaling and reduce body weight and/or hunger in patients with HO.

3.2. Setmelanotide

Setmelanotide is a synthetic, cyclic octapeptide (8-amino acid-containing peptide) that functions as a potent MC4R agonist. Setmelanotide is an 8-amino acid, cyclic peptide that binds with high affinity (inhibitory constant = 2.1 nM) to the human MC4R and is efficient in activating MC4R (50% effective concentration = 0.27 nM). While not an analog, it retains the specificity and functionality of the naturally occurring POMC-derived neuropeptide, α -MSH, which is the endogenous ligand for the MC4R. Setmelanotide is more potent and has a much longer half-life (~10-12 hours in humans) than the short-lived α -MSH ligand.

The setmelanotide peptide was initially selected for clinical development based on its acceptable circulating half-life as a saline formulation (2.8-3.5 hours in non-human primates) and the ability to decrease body weight gain and suppress food intake in normal rats. Subsequent studies demonstrated the efficacy of setmelanotide in suppressing food intake and body weight gain in diet-induced obese mice, rats, dogs, and monkeys, as well as in genetic models of obesity, including leptin-deficient ob/ob mice and leptin receptor deficient obese Zucker rats. Later studies in obese monkeys showed that setmelanotide did not increase blood pressure (BP) or heart rate (HR), a potential concern observed with other MC4R agonist compounds.

To support clinical studies, the toxicological profile of setmelanotide formulations has been evaluated in repeated-dose continuous SC infusion toxicity studies up to 13 weeks in duration in rats and monkeys. The formulation used in almost all of these studies, including the pivotal 28-day and 13-week toxicology studies, was setmelanotide in 0.9% sodium chloride for injection (setmelanotide-saline formulation), tested over a range of concentrations. An International Council for Harmonisation (ICH)-compliant battery of in vitro and in vivo genetic toxicity studies that included a bacterial mutation assay, a chromosomal aberration assay in cultured human peripheral blood lymphocytes and a rat micronucleus study has been completed with this formulation. In addition, a 7-day repeat dose local tolerability bridging study was conducted with the current clinical formulation, setmelanotide-mPEG/DSPE (N-[Carbonyl-methoxypolyethylene glycol 2000]-1,2-distearoyl- glycero-3-phosphoethanolamine sodium salt) in rodents.

Finally, chronic toxicology, reproductive, and juvenile toxicology studies using the RM-493-mPEG/DSPE formulation are completed and reports are in preparation.

The most significant potential safety issue for MC4R agonist compounds is the concern about potential mechanism-based increases in HR and BP. An MC4R agonist, LY2112688 (Eli Lilly and Company), had been studied in the clinic and caused HR and BP increases at all doses (eg, up to a mean 9.4 mm Hg increase in systolic BP [SBP] at the highest dose) [Greenfield 2009, Kievit et al 2013]. While the increases were not an immediate safety concern for the healthy volunteers in the Lilly study, similar but chronic increases in a patient population with obesity would have been problematic.

Setmelanotide was developed in nonclinical studies to analyze and obviate these cardiovascular (CV) effects. A large number of nonclinical studies were performed to demonstrate that setmelanotide did not cause similar CV effects as LY2112688, while still delivering equal or greater efficacy in animal models. The underlying premise of the development program was that setmelanotide in humans would deliver efficacy on weight loss without unacceptable CV effects.

A review of the clinical effects of setmelanotide revealed little if any evidence of BP or HR change from baseline versus placebo in any study, nor evidence of a pharmacokinetic/pharmacodynamic relationship [[Gottesdiener 2015](#)].

Other potential safety and/or tolerability issues that have been reported from published literature for some MC4R agonists in clinical and animal studies have included nausea and vomiting, male penile erections, increases in female sexual arousal, and off-target activity at the closely related MC1R (which mediates melanin deposition in the skin, producing tanning). In addition to careful CV monitoring, the setmelanotide program was designed to include careful monitoring for these potential mechanism-based effects in the initial clinical studies.

Overall, ~600 subjects have been exposed to setmelanotide or matching placebo at doses ranging from 0.0025 to 0.1 mg/kg/24 hours (0.12-9.12 mg total daily dose) in the setmelanotide clinical development program. (The exact number is not known, due to ongoing double-blinded clinical studies.) Overall, setmelanotide has been well tolerated by subjects who have received it in clinical studies. Regardless of formulation, setmelanotide has demonstrated a mostly similar set of adverse events (AEs) in both short-term and long-term clinical studies. Treatment-emergent adverse events (TEAEs) associated with setmelanotide include injection site reactions, intermittent and short-duration gastrointestinal AEs (mostly mild in grade, including reduced appetite, nausea, diarrhea, and vomiting), gradual and reversible increases in skin and nevi pigmentation, and short duration, intermittent male penile erections.

Data obtained to date in the setmelanotide clinical program demonstrate robust weight reduction and hunger suppression efficacy in obesity disorders impacting the leptin-melanocortin pathway, with proof-of-concept established for obesity associated with POMC deficiency, LEPR deficiency, Bardet-Biedl syndrome, and Alström syndrome. By restoring impaired signaling in this pathway, setmelanotide can serve as an indirect form of replacement therapy for patients with hypothalamic deficiencies leading to extreme obesity, with the potential for dramatic improvements in body weight and appetite control.

3.3. Benefit/Risk Assessment

Setmelanotide has not been investigated previously in patients with HO, a population of patients with no effective long-term therapeutic options [[Abuzzahab 2019](#)]. However, in patients with rare genetic forms of obesity, setmelanotide has been associated with clinically meaningful reductions in weight and improvement in hunger. In particular, in patients with POMC or LEPR deficiency obesity, who are characterized by early onset obesity, severe hunger and progressive weight gain, setmelanotide has demonstrated clinically meaningful and statistically significant weight reduction, often bringing patients with very high morbid obesity BMI ($>40 \text{ kg/m}^2$) to BMI ranges in the overweight or normal range ($<30 \text{ kg/m}^2$). In addition to weight loss, setmelanotide has demonstrated clinically meaningful and statistically significant decreases in hunger. Both the decreased hunger and the weight loss continue over 52 weeks of treatment and are maintained with continued setmelanotide treatment. Furthermore, following the significant

weight loss with setmelanotide treatment, there were improvements in glycated hemoglobin (HbA1c), glucose and lipids, as well as body composition with decreased fat mass and decreased waist circumference. These weight loss changes were accompanied by improvements in quality of life.

Setmelanotide is well tolerated. Side effects of setmelanotide are predictable, well understood and do not present significant safety concerns. Collectively, safety data obtained to date show that AEs commonly associated with setmelanotide include injection site reactions and skin hyperpigmentation. Less commonly, nausea and vomiting were reported and rarely, sexual events have been observed. Potential mechanistic-based events such as hypertension have been assessed throughout the setmelanotide clinical development program and have not been observed. Events associated with severe obesity such as depression and suicidal ideation occurred infrequently and were assessed as not related to setmelanotide.

Overall, the substantial weight loss, reduction of hunger, and improvement in cardiometabolic parameters, as well as quality of life, represents a clinically significant benefit with minimal safety risk to patients with rare forms of obesity treated with setmelanotide.

In conclusion, it is considered that setmelanotide will have a positive benefit-risk profile in patients with HO who have no long-term successful therapeutic options.

More detailed information about the known and expected benefits and risks and reasonably expected AEs of setmelanotide may be found in the Investigator's Brochure.

4. OBJECTIVES AND ENDPOINTS

The objectives and endpoints are summarized in [Table 2](#).

Table 2: Objectives and Endpoints

Objectives	Endpoints
Primary	

 The primary objective of this study is to evaluate the change in body weight in response to setmelanotide administered subcutaneously (SC) daily in patients with HO. 	
 Proportion of patients with $\geq 5\%$ reduction from baseline in BMI after 16 weeks of setmelanotide treatment compared to a historic control of $< 5\%$ in this patient population.
Secondary	

 The secondary objectives of this study are to evaluate changes in parameters of body weight, body mass index (BMI), waist circumference, and hunger in response to setmelanotide in patients with HO and to evaluate the safety and tolerability of setmelanotide in patients with HO. 	
Key Secondary
 
 Composite proportion of patients aged ≥ 6 to < 18 years with ≥ 0.2 reduction of BMI Z-score and patients aged ≥ 18 years with 5% reduction of body weight from baseline after 16 weeks of setmelanotide Proportion of patients aged ≥ 6 to < 18 years with ≥ 0.2 reduction of BMI Z-score from baseline after 16 weeks of setmelanotide Proportion of patients aged ≥ 18 years with $\geq 5\%$ reduction of body weight from baseline after 16 weeks of setmelanotide 
Other Secondary
 
 Change from baseline in waist circumference in patients aged ≥ 18 years after 16 weeks setmelanotide treatment. Change in hunger in response to 16 weeks of setmelanotide treatment as measured by change from baseline in daily and global hunger scores. Safety and tolerability assessed by the frequency and severity of AEs, vital signs, and laboratory evaluations.

Objectives	Endpoints
[REDACTED]	[REDACTED]

5. STUDY DESIGN

5.1. Overall Design

This is a Phase 2, multicenter, open-label, proof of concept study designed to assess the effect of setmelanotide on weight loss on a population affected by HO. Approximately 15 patients aged 6 to 40 years, inclusive, are planned to be enrolled across approximately 3-5 clinical sites in the United States (US).

Screening Period

Upon providing informed consent, patients will enter the Screening Period, during which they will be assessed for eligibility and complete all screening procedures as described in the Schedule of Activities (SoA) ([Table 1](#)).

Treatment Period

Patients who are determined to be eligible, based on Screening assessments, will return to the clinic for the Baseline Visit (Visit 2) and receive the first setmelanotide dose. The starting setmelanotide dose is dependent on patient age; however, for all patients, the setmelanotide dose will be titrated to a final dose of 3.0 mg/day (initial titration phase), as follows:

Patients aged 6 to <16 years, inclusive

- Starting at Baseline (Day 1; Visit 2) through approximately Day 14, patients will receive setmelanotide 1.0 mg/day.
- Starting at approximately Day 15 through 28, patients will receive setmelanotide 2.0 mg/day.
Patients/caregivers will be contacted by study center personnel on Day 15 to ensure dose titration has occurred and to document any AEs.
- Starting on approximately Day 29 (Visit 3), patients will receive setmelanotide 3.0 mg/day; patients will continue to receive setmelanotide 3.0 mg/day for 12 weeks.

The dose of setmelanotide should be titrated as explained in the SoA.

Patients aged ≥16 years, inclusive

- Starting at Baseline (Day 1; Visit 2) through approximately Day 14, patients will receive setmelanotide 2.0 mg/day.
- Starting at approximately Day 15, patients will receive setmelanotide 3.0 mg/day; patients will continue to receive setmelanotide 3.0 mg/day for 14 weeks.

Patients/caregivers will be contacted by study center personnel on Day 15 to ensure dose titration has occurred and to document any AEs.

The dose of setmelanotide should be titrated as explained in the SoA.

Patients will return to the study center for Visits 3, 4, and 5 (Weeks 4, 8, and 12, respectively), with each of these visits conducted approximately 4 weeks apart. All patients will return to the study center at Week 16 (Visit 6) and receive the last setmelanotide injection. Study endpoints are analyzed at Visit 6. After completion of Visit 6, participation in the current study will then conclude in one of the following 2 ways:

- Patients meeting the primary endpoint may be eligible to be enrolled in a separate extension study, Rhythm Study RM-493-022, under which auspices the patient will continue to receive setmelanotide.
- Patients who do not meet the primary endpoint or elect not to continue setmelanotide are to discontinue setmelanotide at Visit 6 and return for an End-of-Study (EOS) Visit (Visit 7) 4 weeks thereafter for a final safety review under the auspices of the current study.

5.2. Patient and Study Completion

The study is planned to enroll ~15 patients, with ~5 to 10 patients aged >12 years, and up to 10 patients between 6 and 12 years.

A patient is considered to have completed the study if he/she has either:

- Receives the last planned setmelanotide dose at Week 16 (Visit 6), meets the primary endpoint, and elects to enroll in a separate extension study, Rhythm Study RM-493-022, under which auspices the patient will continue to receive setmelanotide.

- Receives the last planned setmelanotide dose at Week 16 (Week 6) and completes the EOS Visit (Visit 7) for a final safety review under the auspices of the current study.

[figure not shown]
Patients who discontinue before completing the 16-week treatment period are to attend a Treatment Discontinuation visit within 7 days (± 4 days) after the last setmelanotide dose for final study assessments.

The end of the study is defined as the date of the last visit of the last patient under the auspices of the current study.

5.3. Scientific Rationale for Study Design

Setmelanotide is being evaluated as a potential treatment for obesity in rare mechanistically induced populations with hypothalamic injury and subsequent obesity.

[figure not shown]
Given the rarity of the condition under study, no placebo control group is planned. Placebo comparisons with so few patients with HO existing, all of whom are expected to demonstrate a very high need for therapy, are not considered feasible.

5.4. Justification for Dose

Based on the results of previous studies in patients with rare genetic forms of obesity, the recommended setmelanotide dose for adults is a starting dose of 2 mg once daily (QD), with, if tolerated for 2 weeks, an increase to 3 mg QD, aiming to achieve a normal BMI.

For adolescents 12 to 15 years of age and pediatric patients 6 to 11 years of age, the recommended starting setmelanotide dose is 1 mg QD, with, if tolerated for 2 weeks, an increase to 2 mg, aiming to achieve a healthy weight 50-90th centile per charts/guidelines. A further escalation to 3 mg QD is required at the end of Week 4 (Day 28). There are 2 main factors supporting this regimen.

5.5. Study Conduct During the COVID-19 (Coronavirus) Pandemic

The worldwide Coronavirus Disease 2019 (COVID-19) pandemic may impact the conduct of clinical studies due to the challenges from quarantines, site closures, travel limitations, and other considerations if site personnel or study participants become potentially exposed to or infected with COVID-19. To assure the safety of study participants, maintain compliance with Good Clinical Practice (GCP), and minimize risks to study integrity, if necessary, in consultation with the Sponsor, the method of assessment may be changed (eg, paper assessments replaced by electronic assessments). In addition, site visits may be replaced with telephone, internet-based video-conferencing applications, or home visits by qualified health care professionals. Normal procedures, as detailed in this protocol, will be resumed as soon as possible thereafter.

More detailed guidance on study conduct during the COVID-19 pandemic is provided in [Appendix 8](#).

6. STUDY POPULATION

Prospective approval of protocol deviations to recruitment and enrollment criteria (ie, protocol waivers or exemptions) is not permitted.

6.1. Inclusion Criteria

Patients must meet all of the following criteria to be eligible for study participation:

1. Patient has documented evidence of HO, including:
 - a. Recent (within the previous 8 months before Screening) evidence of hypothalamic injury on magnetic resonance imaging (MRI); AND
 - b. Diagnosis of craniopharyngioma or other non-malignant brain tumor affecting the hypothalamic region; AND
 - c. Has undergone surgery, or chemotherapy, or radiation ≥ 6 months and ≤ 15 years before Screening.
2. Patient has either unilateral hypothalamic lesions (at least 6 patients) or bilateral hypothalamic lesions (at least 7 patients), as assessed by MRI.

Note: Although the intention of the study is to enroll at least 6 patients with unilateral hypothalamic lesions, the Sponsor may decrease the required number during the course of the study.
3. Aged 6 to 40 years, inclusive, at time of enrollment. (A maximum of 10 patients between the ages of 6 and 12 will be enrolled in the study.)

4. Obesity, documented by a BMI $\geq 35 \text{ kg/m}^2$ for patients ≥ 18 years of age or BMI $\geq 95^{\text{th}}$ percentile for age and gender for patients 6 to <18 years of age based on the US Centers for Disease Control and Prevention criteria.
5. Documented increase in BMI (change from pre-surgery baseline in BMI Z-score ≥ 0.2 for patients <18 years of age or BMI $>5\%$ for patients ≥ 18 years of age) either during the first 6 months following surgery or within 1 year before surgery AND still present at Screening.
6. More than 6 months after the end of post-tumor treatment, including chemotherapy, surgery, or radiation.
7. Patient must meet one of the following contraception requirements:
 - If a female of childbearing potential, defined as fertile, following menarche and until becoming post-menopausal unless permanently sterile (hysterectomy, bilateral salpingectomy, or bilateral oophorectomy), must use a highly effective form of contraception as outlined in Section 9.19.5.
 - If a female of non-childbearing potential, defined as permanently sterile (status post hysterectomy, bilateral oophorectomy, or bilateral salpingectomy) or post-menopausal for at least 12 months (and confirmed with a screening follicle-stimulating hormone [FSH] level in the post-menopausal laboratory range), contraception is not required during the study.
 - Younger female patients who have not reached menarche upon study entry will be assessed for Tanner staging and at first menarche will be required to comply with contraception requirements and pregnancy testing as outlined in the protocol.
 - If a male with female partner(s) of childbearing potential, must agree to a double barrier method if they become sexually active during the study. Furthermore, male patients must not donate sperm during and for 90 days following their participation in the study.
8. Ability to communicate well with the Investigator, understand and comply with the requirements of the study, and understand and sign the written informed consent, or, for patients aged <18 years, a parent/legal guardian that can sign.
9. If receiving hormone replacement therapy (ie, thyroid hormones, glucocorticoids, growth hormone or other medications known to affect metabolism or weight/body composition), the dose of such therapy has remained stable for at least 2 months prior to Screening. (Changes in dose of $\leq 15\%$ may be permissible, with the Sponsor's approval.)

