9.19.5. Pregnancy and Contraception

Setmelanotide has not been completely evaluated in any preclinical Developmental and Reproductive Toxicology Studies to date, therefore, the effects of setmelanotide on embryo-fetal development are unknown at this time.

Females must not be pregnant and must have a negative pregnancy test result at each visit.

Furthermore, it is imperative that all study patients adhere to the contraception requirements as outlined below.

Female patients of childbearing potential, defined as fertile, following menarche and until becoming post-menopausal unless permanently sterile (hysterectomy, bilateral salpingectomy, or bilateral oophorectomy), must use a highly effective form of contraception throughout the study and for 90 days following the study. Highly effective forms of contraception include:

- Combined (estrogen and progestogen) hormonal contraception associated with inhibition of ovulation (oral, intravaginal, or transdermal)
- Progestogen-only hormonal contraception associated with inhibition of ovulation (oral, injectable, implantable)
- Intrauterine device (IUD)
- Intrauterine hormone-releasing system
- Bilateral tubal occlusion
- Vasectomized partner (provided that the vasectomized partner is the sole sexual partner of the woman of childbearing potential (WOCBP), and the vasectomized partner has received medical assessment of surgical success)
- Sexual abstinence, only if it is the preferred and usual lifestyle of the patient

Females of non-childbearing potential, defined as permanently sterile (status post hysterectomy, bilateral oophorectomy, or bilateral salpingectomy) or post-menopausal for at least 12 months (and confirmed with a screening FSH level in the post-menopausal range) do not require contraception during the study. Younger female patients who are not sexually mature at study entry will be assessed for Tanner staging and required to comply with contraception and pregnancy testing requirements at first menarche.

Male patients with female partner(s) of childbearing potential must agree to use contraception (eg, if they have not had a vasectomy then should either (a) abstain from reproductive sexual intercourse or (b) use a single barrier method in combination with a female partner using a highly reliable method (ie, hormonal or IUD) if they become sexually active during the study and for

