90 days following the study. Male patients must not donate sperm for 90 days following their participation in the study.

If a pregnancy should occur while a male or female patient is on study drug, relevant pregnancies will be followed up on to determine birth and neonatal outcomes.

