**Table 2 Protocol deviations**

Deviation
Any patient that does not have a body weight measurement at the primary endpoint visit (Visit 6)
Any patient that does not have an available screening or baseline body weight measurement
Any enrolled patient that reports an eligibility-related protocol deviation.
Any patient with prohibited concomitant treatments/procedures prior to Visit 6 considered to have a substantial impact on the primary efficacy outcome.
Any patient with a prohibited medical history, unstable medical history condition, or medical history condition that worsens prior to Visit 6 considered to have a substantial impact on the primary efficacy outcome.

All protocol deviations will be presented by patient in a data listing. Patients who are excluded from the PP population will also be presented in a data listing, along with their reason(s) for exclusion. Protocol deviation listings will be reviewed, and each patient will be classified as belonging to the per-protocol set or not. Exclusions from the per-protocol set will be identified and documented prior to database lock.

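### Inclusion criterion 7 and Protocol Section 9.19.5 state different contraception rules, for different periods, for sexually active male patients

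*Protocol*

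**What the plan says.** Protocol Section 6.1, item 7, has one bullet for men with partners of childbearing potential. Such a man "must agree to a double barrier method if they become sexually active during the study". The bullet adds that "male patients must not donate sperm during and for 90 days following their participation in the study". The synopsis carries the same text. The list opens by stating that "Patients must meet all of the following criteria to be eligible for study participation", and Section 6 rules out waivers of the enrolment criteria.

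Section 9.19.5 addresses the same men and describes its contraception requirements as imperative for all study patients. It asks them to agree to contraception and gives two routes by way of example, both addressed to men without a vasectomy. The first is abstinence. Under the second, such a man would "use a single barrier method in combination with a female partner using a highly reliable method (ie, hormonal or IUD"). The duty covers the study and a further 90 days. On donation the section says: "Male patients must not donate sperm for 90 days following their participation in the study".

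The bullet in item 7 for females of childbearing potential sends the reader to Section 9.19.5. The male bullet does not.

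**The concern.** Two current and binding parts of the protocol give the same men different instructions on method and on duration, and neither is marked as giving way to the other. A site checking eligibility at entry would use criterion 7. A site counselling a patient during the study would use Section 9.19.5. These can lead to different answers for the same man.

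The main stake is a clear safety instruction. Section 9.19.5 itself says that the effects of setmelanotide on embryo-fetal development are not known, so method and duration should not depend on which page is read. The second stake is a clear eligibility test. All inclusion criteria must be met and waivers are barred, so a site that accepts what Section 9.19.5 accepts could enrol a man who does not meet criterion 7 as worded.

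**Working it through.** No calculation applies. The check sets the passages side by side and then takes each kind of patient through both.

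| Element | Section 6.1, item 7 (and synopsis) | Section 9.19.5 |
|---|---|---|
| Method if sexually active | Double barrier | One barrier plus the partner's hormonal method or IUD, given as an example |
| Vasectomy | Not mentioned | Listed routes apply only to men without one |
| Abstinence | Not mentioned; the duty starts only with sexual activity | Listed as route (a) |
| Contraception period | During the study | During the study and 90 days after it |
| Sperm donation barred | During the study and 90 days after it | 90 days after it; the study period is not stated |
| Reference to the other section | None in the male bullet | None |

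**Each kind of man with a partner of childbearing potential:**

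1. *He stays abstinent.* This is route (a) of Section 9.19.5. The condition in criterion 7 is not triggered. He meets both.
2. *He agrees only to one barrier plus the partner's method.* He meets route (b) of Section 9.19.5. One barrier is not two, so he does not meet the wording of criterion 7.
3. *He is vasectomised and relies on that.* Section 9.19.5 asks him for neither listed route. Criterion 7 makes no exception for him, so he does not meet its wording unless he also agrees to a double barrier.
4. *He agrees to a double barrier during the study and nothing more.* He meets criterion 7. He uses neither listed route of Section 9.19.5 and leaves its 90 days uncovered.
5. *He agrees to a double barrier and continues it for 90 days.* He meets criterion 7. Because the routes in Section 9.19.5 are examples, he can also be read as meeting that section.

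The conflict therefore concerns cases 2, 3 and 4. On sperm donation, a man reading only Section 9.19.5 finds no ban during the study; a man reading criterion 7 does.

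**Link to the analysis.** The Full Analysis Set requires one dose and baseline data (Protocol Section 10.2, SAP Section 5.1) and has no eligibility condition. The primary analysis uses that set (SAP Section 9). SAP Table 2 lists among the reasons for exclusion from the per-protocol set "Any enrolled patient that reports an eligibility-related protocol deviation". The per-protocol analysis is supportive and is run only as needed (SAP Sections 9 and 9.1.1). Nothing in the sample size or power statement depends on the contraception rule.

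**Who could be affected.** Protocol Section 5.2 plans about 15 patients, with up to 10 aged 6 to 12 and about 5 to 10 older than 12. The affected men are the sexually active males within the older group. The documents give neither the sex split nor their number.

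**The case against.** The strongest reply is that this is loose wording rather than an impossible demand. Section 9.19.5 offers its routes as examples and does not forbid a double barrier, so a man can satisfy both sections by doing more than either asks. Much of the difference in duration is silence in criterion 7, which Section 9.19.5 fills for all patients. The bullet for females of childbearing potential also omits the 90 days and simply points to Section 9.19.5. That the two can be met together stands. It does not remove the point: no text tells a man to combine the two rules, and the male bullet lacks the pointer that fills the gap for women.

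Three stronger readings are tempting, and the documents do not support them.

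- *Every man who follows Section 9.19.5 fails the inclusion criterion.* Abstinence is one of its routes and does not breach criterion 7.
- *Such a man is removed from the per-protocol set.* Criterion 7 tests what he agrees to at entry. A man who agreed to a double barrier and later used another route met the criterion when enrolled, and his later conduct is not clearly eligibility-related. Exclusion would need enrolment on route (b) or vasectomy alone and a reported deviation. SAP Section 7 says a deviating patient might be excluded, depending on seriousness. On the other hand, the eligibility line in Table 2 carries no qualifier about impact, so exclusion remains possible.
- *Each affected man costs 1/15 = 6.7% of the sample.* The division is right, but the primary analysis keeps him, and the per-protocol analysis may not be run. The figure measures no effect on the result.

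Two limits on the safety argument also stand. Section 3.2 says reproductive toxicology studies are completed with reports in preparation, which sits uneasily with the statement in Section 9.19.5 that the effects are unknown. The consent forms are not among the documents reviewed, so what patients were actually told cannot be judged.

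**Conclusion.** The point holds as a contradiction within the protocol on male contraception: in method, in duration, and in the sperm-donation period. It applies to sexually active men with partners of childbearing potential who agree only to the single-barrier route, who rely on vasectomy, or who follow criterion 7 alone.

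Its size is a matter of clear instruction and consistent eligibility, not of statistics. The primary analysis, the power statement and the Full Analysis Set are unaffected, and any per-protocol effect depends on a deviation being reported. The conclusion assumes that Section 9.19.5, by limiting its routes to men without a vasectomy, treats vasectomy as sufficient; that is the natural reading but is not stated outright. It does not depend on whether embryo-fetal effects are in fact unknown, because two conflicting binding rules need reconciling either way. The documents do not show which rule was intended.

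**What to change.** Reconcile the synopsis, Section 6.1 item 7 and Section 9.19.5 so that they state one male contraception rule (including how vasectomy and abstinence are treated), one duration, and one period for the ban on sperm donation. Have the male bullet in item 7 refer to Section 9.19.5, as the bullet for females of childbearing potential already does, so that the rule is stated in full only once. The sponsor decides which rule and which periods apply; none is proposed here.

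The cost is wording in a protocol amendment, with the IRB approval that Appendix 7 requires, and matching consent text if the consent form repeats either rule. No change to the sample size, the data collected or the planned analyses is needed.
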